6.4.2 Safety Endpoints

The safety endpoints for this study are incidence of adverse events (AEs) and changes in clinical laboratory values, electrocardiogram (ECGs), vital sign, and Eastern Cooperative Oncology Group (ECOG) measurements.

6.4.2.1 Adverse Events

An AE is any untoward medical occurrence in a clinical study participant, temporally associated with the use of study drug, whether or not considered related to the study drug. An AE can therefore be any unfavorable and unintended sign (including an abnormal laboratory finding), symptom, or disease (new or exacerbated) temporally associated with the use of study drug whether or not related to the study drug. An AE can arise from any use of the study drug and from any route of administration, formulation, or dose, including an overdose.

AEs will be captured from the time of the first study drug administration through the Safety Follow-up Visit.

6.4.2.2 Laboratory Parameters

All protocol-required local laboratory tests, as defined in Table 9, will be conducted in accordance with local laboratory practices.

Laboratory	Parameters
Tests	
Hematology	Platelet count
	Hemoglobin
	WBC (leukocyte count including differential):
	Neutrophils (ANC, calculated from the leukocyte count and WBC differential count)
	Lymphocytes
	Monocytes
	Eosinophils
	Basophils
	% Blasts

 Table 9
 Protocol-Required Safety Laboratory Tests

Laboratory	Parameters
Tests	
Clinical	Blood urea nitrogen/urea
chemistry	Creatinine
	CO ₂
	Uric acid
	Albumin
	Sodium
	Phosphorus
	Triglycerides
	Total cholesterol
	Magnesium
	Calcium
	Potassium
	Chloride
	Glucose
	Amylase
	Lipase
	Total protein
	ALP
	Lactate dehydrogenase
	Total and direct bilirubin
	AST/serum glutamic-oxaloacetic transaminase
	ALT/serum glutamic-pyruvic transaminase
Coagulation	Prothrombin time or international normalized ratio
	Activated partial thromboplastin time/ partial thromboplastin time

Laboratory Tests	Parameters
Routine	Specific gravity
urinalysis	pH
	Protein
	RBC
	WBC
	Leukocyte esterase
	Ketones
	Nitrite
Pregnancy	Highly sensitive serum or urine human chorionic gonadotropin
testing	pregnancy test (as needed for women of childbearing potential) ^a

Abbreviations: ALP = alkaline phosphatase; ALT = alanine aminotransferase; ANC = absolute neutrophil count; AST = aspartate aminotransferase; $CO_2 = bicarbonate$; RBC = red blood cell; WBC = white blood cell

^a Local high-sensitivity urine pregnancy testing will be standard for the protocol unless serum testing is required by local regulation or Institutional Review Board/Independent Ethics Committee.

6.4.2.3 Other Safety Endpoints

6.4.2.3.1 Vital Signs

Vital signs will be measured in a semi-supine position after 5 minutes of rest and will include temperature, systolic and diastolic blood pressure, pulse rate, and respiratory rate.

6.4.2.3.2 Electrocardiograms

Triplicate 12-lead ECGs will be obtained using an ECG machine that automatically calculates the heart rate and measures PR, QRS, QT, and QTc intervals (utilizing Fridericia's correction for QTc).

6.4.3 *Pharmacokinetic Endpoints*

The PK endpoints will be provided in a separate report and is outside the scope of this SAP.

7 STATISTICAL METHODS

7.1 General Methodology

Data will be analyzed by Syros Pharmaceuticals, Inc. biostatistics personnel or designee. Statistical analyses will be reported with tables, figures, and listings, using recommended ICH numbering. Output specifications for all tables, figures, and listings will be in conformance with the guidelines specified by the ICH in Appendix 7 of the *Electronic Common Technical Document Specification* (Apr 2003).

7.1.1 Reporting Conventions

Efficacy tables, safety tables (except overall AE tables), and figures will be summarized by treatment group (tamibarotene + azacitidine and placebo + azacitidine). Other tables will also include a column for all participants combined. In general, all data collected, and any derived data will be presented in participant data listings for the relevant populations. Listings will be ordered by treatment group, participant number, and assessment or event date. The treatment group presented in listings will be based on the planned assignment, unless otherwise noted.

In general, continuous variables will be summarized to indicate the number of participants with available data (n), mean, standard deviation (SD), median, minimum, and maximum values. Categorical variables, unless otherwise specified, will be summarized by the number of participants with available data (n) and number and percentage of participants in each category. If there is a subcategory under a categorical variable, this subcategory will be summarized by the number of participants under this categorical variable. A category for 'Missing' will be added and populated to make the total percentage of each category equal to 100%. Select ordinal data may be summarized using both descriptive statistics and counts and percentages of participants in each category, as appropriate.

Non-zero percentages will be rounded to 2 decimal places. Rounding conventions for presentation of summary statistics will be based on the precision of the variable of summarization, as it is collected in its rawest form (i.e., on the electronic case report form [eCRF] or as provided within an external file) and are outlined as follows:

- The mean and median will be rounded to 1 more decimal place than the precision of the variable of summarization, and up to 3 decimal places.
- Measures of variability (e.g., SD, SE) will be rounded to 2 more decimal places than the precision of the variable of summarization, and up to 4 decimal places.
- Minimum and maximum values will be presented using the same precision as the variable of summarization, and up to 2 decimal places.

Other statistics (e.g., CIs) will be presented using the same general rules outlined above or assessed for the most appropriate presentation based on the underlying data.

The primary endpoint will be tested at a full alpha level of 2.5%. To control the overall Type I error rate of the primary and key secondary endpoints, hierarchical testing will be performed in the following order: (1) primary endpoint; (2) key secondary endpoint. If hypothesis testing of the primary endpoint is rejected, the key secondary endpoint will be tested at the full alpha level of 2.5%; otherwise, the testing will be stopped. Secondary and exploratory efficacy endpoints will be tested using a two-sided, 5% significance level, and two-sided 95% CIs will be reported when appropriate, unless otherwise specified. P-values will be rounded to 4 decimal places. P-values less than 0.0001 will be displayed as "<0.0001"; p-values greater than 0.9999 will be displayed as ">0.9999".

When applicable, analyses will be stratified by IPSS-R risk group (Intermediate, High, and Very High Risk) and by geographical region (North America, Western Europe, plus Israel, and Eastern Europe).

7.1.2 Summarization by Visit

Scheduled analysis visits are visits at scheduled timepoints as specified in the protocol. Data summarized by study visit will be based on the nominal, scheduled visit label as reported on the eCRF. For safety analysis, in the case of multiple observations at a specific visit, the latest observation will be used. If more than 1 observation is made on the same day, an average value if continuous or the worst value if categorical will be included in the analysis.

Data collected at unscheduled visits will not be included in the by-visit summaries but will be considered when endpoint derivations potentially include multiple visits (e.g., determination of baseline value, determination of worst post-baseline value, etc.). All data will be included in participant listings.

7.1.3 Data Handling Rules

7.1.3.1 Threshold Values

Unless otherwise noted, values that include a threshold sign (i.e., '<' or '>') will be imputed for summary tables in the following manner:

• A value that is 1 unit less than the limit of quantitation will be used for the calculation of descriptive statistics if the datum is reported in the form of "<x" (where x is considered the limit of quantitation). For example, if the values are reported as <50 and <5.0, values of 49 and 4.9, respectively, will be used for calculation of summary statistics. An exception to this rule is any value reported <1. For the values reported as <1 or <0.1, a value of 0.9 or 0.09 will be used for calculation of summary statistics.
- A value that is 1 unit above the limit of quantitation will be used for the calculation of descriptive statistics if the datum is reported in the form of ">x" (where x is considered the limit of quantitation). Values with decimal points will follow the same logic as above.
- The limit of quantitation will be used for the calculation of descriptive statistics if the datum is reported in the form of "≤x" or "≥x" (where x is considered the limit of quantitation).

The original data including the threshold signs will be displayed in the listings.

7.1.3.2 Baseline Definition

For all endpoints, unless otherwise specified, the baseline value will be the latest pre-dose assessment with a non-missing value, including those from unscheduled visits. If time is not collected, Day 1 assessments are assumed to be taken prior to first dose and used as baseline. When scheduled assessments and unscheduled assessments occur on the same day of first dose and time of the assessment or time of first dose is not available, the following convention to determine baseline will be used:

- If both a scheduled and an unscheduled visit are available on the day of the first dose, and time is missing, the scheduled assessment will be used as baseline.
- If all scheduled assessments are missing on the day of the first dose and an unscheduled assessment is available, the unscheduled assessment will be used as baseline.

For participants who did not receive study treatment during the study, baseline will be defined as the latest, non-missing collected value. Unless otherwise stated, if baseline data are missing, no derivation will be performed, and baseline will be set to missing.

For ECG analyses, if the latest, non-missing pre-dose value is from triplicate, the participant level baseline is defined as the mean of the triplicate baseline assessments.

7.1.3.3 Imputation of Partial or Missing AE Dates for Analysis

Rules for imputing partial or missing AE dates for analysis are provided in Table 10.

Adverse Events	Partial/missing AE dates recorded in the CRF will
	be imputed using the following conventions:

Missing start day	The first of the month will be used unless it is before
	the start date of study treatment; in this case, the study
	treatment start date will be used and hence the event is
	considered treatment emergent.
Missing start day and month	No imputation.
Missing end day	Last day of the month will be used.
Missing end day and month	No imputation.
Completely missing start/end	No imputation.
day	

Abbreviations: AE = adverse event; CRF = case report form

7.1.3.4 Imputation of Partial or Missing Medical History/Concomitant Medication Dates for Analysis

Rules for imputing partial or missing medical history or concomitant dates for analysis are provided in Table 11.

Table 11Date Imputation Rules for Medical History/Prior and Concomitant
Medications/Prior Cancer Therapy

Medical History/Prior and Concomitant Medications/Prior Cancer Therapy	Partial/Missing Medical History/Prior and Concomitant Medication/Prior Cancer Therapy Dates Recorded in the CRF Will Be Imputed Using the Following Conventions:
Missing start day	'01' will be used for the day.
Missing start day and month	'01' will be used for the day and 'Jan' will be used for the month.
Missing end day	 '28/29/30/31' will be used for the day (dependent on the month and year) and the earlier of last day of the month and the end of study date will be used as the imputed value except in the following two cases: 1) For prior cancer therapy 2) If it is not ongoing and the start date is prior to the study treatment start date For these two cases, the end date will be imputed as (study treatment start date -1).

Version 4.0

Missing end day and month

'31' will be used for the day and 'Dec' will be used for
the month, and the earlier of 31 Dec of the given year
and the end of study date will be used as the imputed

	and the end of study date will be used as the imputed
	value except in the following two cases:
	1) For prior cancer therapy
	2) If it is not ongoing and the start date is prior to the
	study treatment start date
	For these two cases, the end date will be imputed as
	(study treatment start date -1).
Completely missing start/end	No imputation.
day	

Imputation of Partial or Missing New Anticancer Therapy Dates for 7.1.3.5 Efficacy Evaluation

Start dates for follow-up anticancer therapy will be temporarily imputed in order to define event and censoring rules for EFS, response rate, time to event, duration of response, or time to response (e.g., start date for new anticancer therapy). The imputed dates will be stored in the anticancer therapy-derived dataset.

- If missing start day, month, and year, then no imputation.
- If missing start day and month, then no imputation.
- If missing start day only, then do the following: •
 - If partial date falls in the same month as the last dose of study treatment, then assign to earlier of (date of last dose of study treatment + 1, last day of month).
 - If partial date falls in the same month as the participant's last assessment and the participant's last assessment is transformation to AML, then assign to earlier of (date of transformation to AML + 1, last day of month).
 - If both rules above apply, then assign to latest of the 2 dates.
 - Otherwise, impute missing day to the first of the month.
- If missing end date, then no imputation should be done.

7.1.3.6 Imputation of Partial or Missing Date of Birth and the Calculation of Age

Age in years will be calculated as (date of main informed consent – date of birth +1)/ 365.25 and will be stored in the adsl dataset.

- If missing day, month, and year of birth, then no imputation.
- If missing day and month of birth, then impute date of birth to June 30.
- If missing day only, then impute date of birth to 15th of the month. •

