7.3.7 Prior and Concomitant Medications

Medications will be coded using the WHO Drug Dictionary Global B3 Sept. 1, 2020 or a more recent version. Medications entered on the eCRF will be mapped to ATC drug class (level 4) and drug name.

Syros Pharmaceuticals, Inc. SY-1425-301

Prior and concomitant medications will be summarized separately, and the study phase of each medication will be determined programmatically based on medication start and end dates. A prior medication is defined as any medication taken with an end date prior to the first dose of study drug. A concomitant medication is defined as any medication that (1) started before the first dose of study drug and was continuing at the time of the first dose of study drug, or (2) started on or after the date of the first dose of study drug through 30 days after the participant's last dose of study drug.

For both prior and concomitant medication summaries, the number and percentage of participants receiving any medication will be summarized by treatment group and overall, as will the number and percentage of participants receiving any medication by ATC drug class and generic drug name. Participants reporting use of more than 1 medication at each level of summarization (any medication received, ATC class, and generic drug name) will be counted only once. ATC class terms will be displayed in descending order of incidence for all participants, as will generic drug names within each ATC class. The study phase during which each medication was received (e.g., prior or concomitant) will be presented on the listing of prior and concomitant medications.

mITT and ITT analysis sets will be used for prior and concomitant medication analysis.

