8.1.2 Missing Data and Imputation Rules

In Section 7.1.3.4, Table 11 has been updated to ensure that proper imputation methods are used for both events that should end prior to the treatment start date (e.g., prior cancer therapy) and events that should end after the treatment start date (e.g., concomitant medications). Section 7.1.3.6 was added to detail the imputation rules for missing date of birth and the calculation of age. Sections 7.1.3.7, 7.1.3.8, and 7.1.3.9 were added to detail the imputation rules for missing date of missing date of death, calculation of ECG data, and post-baseline missing values, respectively.

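### Table 11 of the SAP sets certain partial end dates to the day before first dose even when the recorded month or year contradicts that date, so some concomitant medications are tabulated as prior

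*SAP*

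**What the plan says.** Table 11 in SAP Section 7.1.3.4 covers medical history, prior and concomitant medications, and prior cancer therapy. When only the end day is missing, the default keeps the recorded month: "the earlier of last day of the month and the end of study date will be used as the imputed value except in the following", after which the table lists a pair of situations. The first case is "1) For prior cancer therapy". The second is "If it is not ongoing and the start date is prior to the study treatment start date". For both, "For these two cases, the end date will be imputed as (study treatment start date -1"). The row for a missing end day and month has the same structure: 31 December of the recorded year, or end of study if earlier, with the same two exceptions. A completely missing date is not imputed.

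Section 7.3.7 then uses the dates: "the study phase of each medication will be determined programmatically based on medication start and end dates". On the prior side, "A prior medication is defined as any medication taken with an end date prior to the first dose of study drug". On the concomitant side, the first limb is a medication that "started before the first dose of study drug and was continuing at the time of the first dose of study drug".

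Section 8.1.2 gives the reason for the Version 4.0 change to Table 11. Suitable methods were wanted both for events that should end before treatment start, such as prior cancer therapy, and for "events that should end after the treatment start date (e.g., concomitant medications").

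**The concern.** An imputation rule should fill in what is missing and leave alone what was collected. The two exceptions do not do that. They test the type of record, or its start date and ongoing status, and then assign a fixed date. The recorded end month or year is never consulted, so the derived date can lie outside the period that the site entered.

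For medications this can change a tabulated result. A drug taken before first dose and stopped during the study is given an end date before first dose, and the program counts it as prior. Among records whose class changes, the error runs one way: concomitant use is lost. Drugs that the protocol prohibits or cautions against on study (Protocol Sections 6.8.3, 6.8.4, 6.8.10 and 6.8.11) are among those that could be affected.

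For prior cancer therapy the class does not change, but the derived end date moves to the eve of first dose, however long ago the therapy ended.

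**Working it through.** The documents state no figure for this rule, so the check applies Table 11 and the Section 7.3.7 definitions to example records. Two dates are assumed: first dose 15 Mar 2023 and end of study 31 Dec 2025. UNK marks a missing day or month.

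Rules applied:

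- Table 11 as written: if the record is prior cancer therapy, or is not ongoing and started before 15 Mar 2023, then end = 15 Mar 2023 − 1 day = 14 Mar 2023. Otherwise end = the earlier of the last day of the recorded month (or 31 Dec of the recorded year) and 31 Dec 2025.
- Comparison: the default for every record, with prior cancer therapy capped at 14 Mar 2023.
- Class (Section 7.3.7): prior if end < 15 Mar 2023; otherwise concomitant.
- Shift = Table 11 end date − comparison end date.

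| Record | Table 11 | Comparison | Shift |
|---|---|---|---|
| (a) Medication, 10 Jan 2023 to UNK Jun 2023 | 14 Mar 2023, prior | 30 Jun 2023, concomitant | −108 days |
| (b) Medication, 10 Jan 2023 to UNK UNK 2024 | 14 Mar 2023, prior | 31 Dec 2024, concomitant | −658 days |
| (c) Medication, 10 Jan 2023 to UNK Mar 2023 | 14 Mar 2023, prior | 31 Mar 2023, concomitant | −17 days |
| (d) Medication, 1 Dec 2022 to UNK Jan 2023 | 14 Mar 2023, prior | 31 Jan 2023, prior | +42 days |
| (e) Prior cancer therapy to UNK Jun 2020 | 14 Mar 2023 | 30 Jun 2020 | +987 days |
| (f) Medication, 1 Apr 2023 to UNK Jun 2023 | 30 Jun 2023, concomitant | 30 Jun 2023, concomitant | 0 |

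Arithmetic for (a): 14 Mar to 30 Jun 2023 is 17 + 30 + 31 + 30 = 108 days. For (e): 30 Jun 2020 to 30 Jun 2022 is 730 days, and from there to 14 Mar 2023 is 257 days. The total is 987 days, and 987 / 365.25 = 2.70 years.

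In (a) and (b) the true end date is certainly after first dose, because every day of June 2023 and of 2024 is later than 15 Mar 2023. Both drugs were therefore being taken at first dose and are concomitant by the SAP's definition, yet Table 11 makes them prior. In (c) the class is genuinely uncertain, since the drug may have stopped before or after 15 March. In (d) the class is right but the derived date contradicts the recorded month. Record (f) shows that a drug started after first dose is unaffected.

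**The case against.** The strongest objection is that the second exception does not say when ongoing status is judged. If it means not ongoing at treatment start, records (a) and (b) escape the exception and receive 30 Jun 2023 and 31 Dec 2024. Section 8.1.2 suggests that this was the aim. But Table 11 does not say so, and a programmer following its wording would produce the results above. Even on that reading, record (d) is still moved out of its recorded month, and the prior cancer therapy exception is untouched.

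The reach is also narrow, and this part of the objection stands in full. Records marked ongoing are exempt, completely missing end dates are not imputed, and records started on or after first dose are unaffected. Protocol Section 8.2.1 requires start and end dates for every medication up to the Safety Follow-up Visit, so partial on-study stop dates may be few. It would be wrong to infer that continuing medications in general become prior.

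A reader might also infer that washout or time since prior therapy would be misreported in tables and listings, or that patients would appear to breach the two-year disease-free criterion. The documents do not support that. Section 7.3.6 tabulates prior cancer therapy by drug class and name only, and no washout or time-since-therapy output is planned. The SAP does not say that listings print imputed rather than recorded dates. Eligibility is reviewed and approved before randomization (Protocol Section 1.3, footnote i), not through these imputed dates. Protocol deviations have their own review under SAP Section 7.3.2, which is not tied to Table 11.

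Finally, removing the exception without a replacement would create the opposite error. A drug stopped before first dose but in the same month would be counted as concomitant. The fix has to deal with that.

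**Conclusion.** The point holds as a minor one. As written, Table 11 overrides a recorded month or year in its two excepted cases. For a medication started before first dose and stopped in a known later month, the prior or concomitant class is then wrong by the SAP's own definition and against the purpose stated in Section 8.1.2. For prior cancer therapy the derived end date can be late by years, about 2.7 in the example.

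The effect stops at the descriptive medication summaries and derived end dates. Subsequent anticancer therapy, deaths and adverse events have their own date rules (Sections 7.1.3.5, 7.1.3.7 and 7.1.3.3), and CR, OS and EFS do not depend on Table 11. The conclusion rests on the literal reading of the second exception. The day counts rest on the assumed dates. The number of affected records cannot be obtained from the documents.

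**What to change.** Rewrite the two end-date rows of Table 11:

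1. For all records, keep the recorded month and year. Impute to the last day of that month, or to 31 December of that year if the month is also missing, capped at the end of study date.
2. For prior cancer therapy, replace the result with first dose minus 1 only when the imputed date would fall on or after first dose.
3. For other records whose partial date spans first dose (same month, or same year with the month missing), state one convention: class as concomitant unless the CRF indicates that the drug stopped before first dose.

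With this wording, records (a) and (b) become concomitant, (d) ends on 31 Jan 2023, (e) ends on 30 Jun 2020, and (c) is decided by the CRF or, failing that, counted as concomitant.

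The cost is the table wording and the derivation code. The downside is that a few drugs stopped shortly before first dose may be counted as concomitant. Such records can be checked individually where the drug is one that had to be stopped before study treatment.

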An End of Treatment (EoT) Visit should occur within 3 days of the last dose of study drug (or within 3 days of decision to permanently stop drug treatment, if this decision directly follows a period when study drug has been on hold) and before the start of any subsequent anticancer therapy. A Safety Follow-up Visit should occur 30 days (±3 days) after the EoT Visit and if possible before the start of any subsequent anticancer therapy. After the EoT Visit, participants who have not progressed/relapsed will enter the Disease Follow-up period, during which response assessments will be performed for up to 5 years after discontinuation of study drug (irrespective of initiation of HSCT or other subsequent anticancer therapy) or until disease progression/relapse, death, or the occurrence of the expected number of OS events to support the final OS analysis, whichever occurs first. It is estimated that a final analysis of OS will occur approximately 70 months following the enrollment of the first participant.

Participants who progress/relapse will enter Survival Follow-up and will be followed to document the start of subsequent anticancer therapy, the date of transformation to AML, the date of death, and OS status until the expected number of OS events to support the final OS analysis is observed.

An Independent Data Monitoring Committee (IDMC) will be established and will review the data at the 2 planned interim futility analyses and the safety interims, as specified in the IDMC Charter.

Figure 1 Study Design

Abbreviations: MDS = myelodysplastic syndrome; RARA = retinoic acid receptor alpha

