5	New anticancer therapy other than HSCT started prior to documented disease progression/relapse or death	Date of last adequate response assessment prior to start of new anticancer therapy other than HSCT	Censored
6	HSCT started prior to documented disease progression/relapse or death	Date of last adequate response assessment occurring prior to documented disease progression/relapse or death, irrespective of HSCT date ^[2] Date of assessment of disease progression/relapse or death ^[SA]	Censored Event
7	Death without an extended loss-to-follow-up time ^[1]	Date of death	Event
8	Death or developed disease progression/relapse after an extended loss-to-follow-up time (≥2 missed consecutive assessment) ^[1]	Date of last adequate response assessment ^[2] prior to the ≥2 missed consecutive assessments	Censored

Abbreviations: CR = complete remission; HSCT = hematopoietic stem cell transplantation

^[SA] Alternative rule for handling of events for DOCR.

^[1] Extended loss-to-follow-up time is defined as the last non-missing adequate response assessment and event (death or disease progression/relapse). Extended loss-to-follow-up time is 208 days. This cutoff is calculated based on the protocol scheduled procedure: the 28-day treatment cycle has ± 3 days window, response assessment is expected to be conducted every 3 months (with ± 14 days window). Thus, 2 consecutive scheduled assessments window is $2 \times [(30 \times 3 + 14] = 208$ days. Within extended loss-to-follow-up time is defined as ≥ 208 days; after an extended loss-to-follow-up time is defined as ≥ 208 days.

^[2] An adequate assessment is defined as an assessment where the Investigator performed all the procedures required for assessment and documented the outcome.

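### SAP 7.1.3.5 has no progression/relapse counterpart to its AML rule, so a same-month relapse can fall after an imputed therapy start and be censored out of DOCR and the other response durations

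*SAP*

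**What the plan says.** SAP 7.1.3.5 states its purpose as follows: "Start dates for follow-up anticancer therapy will be temporarily imputed in order to define event and censoring rules for EFS, response rate, time to event", with duration of response and time to response also listed. When only the day is missing, three rules apply.

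- **Last dose in the same month:** "then assign to earlier of (date of last dose of study treatment + 1, last day of month".
- **Last assessment in the same month, and that assessment is an AML transformation:** the start goes to the earlier of the AML date + 1 and the month's end. If both rules apply, the later date is used.
- **Anything else:** "Otherwise, impute missing day to the first of the month".

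The imputed date matters in Table 13 (DOCR, also used for duration of CR/PR) and Table 14 (duration of overall response). Situation 5 in both tables is: "New anticancer therapy other than HSCT started prior to documented disease progression/relapse or death". The outcome is censoring, and Table 13 gives the date as: "Date of last adequate response assessment prior to start of new anticancer therapy other than HSCT". Table 14 uses nearly the same words. HSCT is handled separately in situation 6. SAP Table 5 supports this with a hypothetical strategy for non-HSCT therapy begun before relapse.

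SAP 6.1 says the End of Treatment (EoT) Visit should take place within 3 days of the last dose, or of the decision to stop after a dose hold, and "before the start of any subsequent anticancer therapy".

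**The concern.** The AML rule keeps the natural order of events: the disease event is found, then the next therapy starts. AML transformation is an EFS event. The response durations end at progression or relapse, and those events have no matching rule. A therapy given because of a relapse can therefore be dated before it. The patient then appears to have switched therapy before relapsing, which is the intercurrent event that the hypothetical strategy is meant to censor.

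The error runs one way. For a therapy that follows the last dose, both dates that can apply to a relapse (the 1st of the month, or last dose + 1) are the earliest possible. An event becomes a censored observation at an earlier date, and the Kaplan-Meier estimate of duration rises. It affects patients who relapse and move quickly to another therapy, within a responder subset where a few lost events could move a median.

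**Working it through.** The plan gives no figure on this point. The only number in these tables' notes is the 208-day cutoff, which reproduces as 2 × (30 × 3 + 14) = 208 and does not bear on the ordering.

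**Worked dates under the rule as written** (therapy recorded as the month only)

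- Last dose 20 January, relapse 15 March, therapy in March. Imputed start 1 March, so the relapse is censored. Had the 15 March finding been AML transformation, the imputed start would be 16 March and the order kept.
- Last dose 10 March, relapse on or before 11 March. Imputed start 11 March, not before the relapse, so the event is kept.
- Last dose 10 March, relapse at the EoT Visit on 12 or 13 March. Imputed start 11 March, so the relapse is censored, although the EoT Visit should precede new therapy.
- Relapse in an earlier month than the therapy. No reversal is possible.

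**Enumeration over the 365 relapse dates of a non-leap year**

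Let g be the true gap in days from relapse to therapy start. A relapse is lost when the imputed start is strictly before it. If the last dose is on or after the relapse, or the day before it, none are lost.

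If the last dose is 2 or more days earlier, a relapse is lost when therapy falls in the same month and the relapse is not on the 1st. In a month of n days that is n − g − 1 dates (never below 0). Relapse and therapy share a month on n − g dates. Summed over 12 months:

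| Gap g (days) | Same month | Relapse lost |
|---|---|---|
| 1 | 353/365 = 97% | 341/365 = 93% |
| 7 | 281/365 = 77% | 269/365 = 74% |
| 14 | 197/365 = 54% | 185/365 = 51% |
| 21 | 113/365 = 31% | 101/365 = 28% |
| 28 | 29/365 = 8% | 18/365 = 5% |

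For g = 1 to 21 the lost count is 365 − 12(g + 1). At g = 28, seven 31-day months give 2 each, four 30-day months give 1 each and February gives 0: 14 + 4 = 18. Nearly every same-month case is lost.

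**Effect on a median (illustration on assumed values)**

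Durations were simulated as exponential with a true median of 12 months. A fraction f of events was moved back to the previous 3-month assessment and censored.

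| f | Kaplan-Meier median (months) | 12/(1 − f) |
|---|---|---|
| 5% | 12.6 | 12.6 |
| 10% | 13.2 | 13.3 |
| 20% | 14.6 | 15.0 |

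The last column is a rough check that treats f as a proportional cut in the event rate. Neither the 12 months nor f comes from the documents.

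**With the rule extended to relapse**, wrongly censored relapses fall to 0% in every scenario run.

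**The case against.** The strongest reply is that the last-dose rule already covers the usual on-treatment sequence. Relapse is a reason to stop study drug (protocol 7.1), so the last dose often falls on or after the relapse, or the day before it, and the order is then kept. This stands. A reader might infer that AML transformation is the only protected case and that relapses leading to new therapy are generally lost. The documents do not support that. What remains exposed is relapse in Disease Follow-up, relapse after a dose hold, and EoT assessments 2 to 3 days after the last dose.

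A reader might also take the percentages as patient rates. They are conditional on a missing day, a non-HSCT therapy and the dosing gap. The documents give no count of partial dates, and it may be very small.

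A third tempting reading is that the primary endpoint is at risk, because 7.1.3.5 lists response rate among its uses and a CR first seen at an EoT marrow could be dated after the imputed therapy. This is not established. SAP 6.4.1.1 says CR should be confirmed at least 4 weeks from marrow sampling. A patient starting therapy later in the same month generally could not have that confirmation beforehand, whatever day is imputed.

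The consequence is also limited. The endpoints are summarised by arm in responders with no between-arm test, and the rule is the same in both arms. OS (Table 12) uses no therapy dates, and EFS situation 6 sets its date without regard to the therapy date. Finally, protocol Table 4 uses treatment policy for subsequent therapy in these durations. Under that strategy the imputed date would not matter; the SAP's hypothetical strategy makes it decisive. That explains how the gap arises but does not close it.

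**Conclusion.** The gap is real but narrow. Applied as written, 7.1.3.5 with situation 5 turns some genuine relapses into earlier censoring, and no other rule in the SAP restores the order. All of these conditions are needed:

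- only the start day is missing;
- the therapy is not HSCT;
- it falls in the same calendar month as the progression or relapse;
- the last dose was at least 2 days before that event.

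When all hold, the relapse is lost unless it fell on the 1st of the month. The bias is upward in DOCR, duration of CR/PR and duration of overall response. Its size in this trial cannot be stated, because neither the number of partial dates nor the number of affected responders is given. The conclusion assumes that a same-day start is not prior to the relapse, and that situation 5 takes precedence when a relapse also fits situation 2 or 3, as the hypothetical strategy implies. It is worth correcting because DOCR describes the durability of the primary endpoint and the stated rule gives a wrong answer, even though no formal test depends on it.

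**What to change.** Extend the second bullet of SAP 7.1.3.5. If the partial date falls in the same month as a documented disease progression, relapse or AML transformation, assign the start to the earlier of that date + 1 and the last day of the month. Where the last-dose rule also applies, take the latest of the resulting dates. Use the 1st of the month only when none of these dates falls in that month.

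The cost is one SAP sentence and a small programming change. It needs no new data and can be made before database lock without knowledge of treatment. The downside is that a therapy truly started earlier in that month than the relapse would be dated slightly late, and that relapse would count as an event.
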